14.1.3. Psoriasis patients

Protocol Activity	Base- line				ı	n Clinic	Period								0	ut Pati	ent Vi	isits					
					Day 1			Day 2	Day 3	Day 4	Day 8												П
	Day -			2 hour post- infusion start	4 hour post- infusion start	post-	post-	24 hour post- infusion start	post-	post-			Day 15	Day 18	Day 22	Day 25	Day 29	Day 36 n	Day 43	Day 57	Day 71 n	Day 85	Day 121
Window											±1d	±1d	±1d	±1d	±1d	±1d	±1d	±1d	±2d	±2d	±2d	±2d	±3d
Admission to the unit	Х																						
Discharge from the unit										Х													
Reassess 2 target lesions for suitability	Х																						
Brief physical	X																						
Urine Drug and Alcohol Screen	X																						
Administer IV Dose (2 hour infusion)			4	→ j																			
Safety Assessme	nts	-	-					-		-		-	-	-			-	-					_
Vital Signs	Χ	Χ		X	X	Х	X	X	X	X	X		Χ		Х		Χ		Х	Х		Χ	Х
12 - Lead ECG	Χk	Х	4	> a		X				X													
Concomitant Medications				∢																			
Adverse Events / SAEs Þ				∢																		,	

Protocol Activity	Base-				n Clinic	Period								Oı	ut Pati	ent Vi	sits					
				Day 1			Day 2	Day 3	Day 4	Day 8												
	Day -		2 hour post- infusion start	4 hour post-	post-	12 hour post- infusion start	24 hour post-	48 hour post-	72 hour post-	168 post-		Day 15	Day 18	Day 22	Day 25	Day 29	Day 36 n	Day 43	Day 57	Day 71 n	Day 85	Day 121
Window										±1d	±1d	±1d	±1d	±1d	±1d	±1d	±1d	±2d	±2d	±2d	±2d	±3d
Efficacy Assessn	nents		-	-	-	-	-				•	•								-		•
Psoriatic Body Surface Area	X											Х				X		X			X	X
Psoriasis Area Severity Index	X											х				x		X			x	X
Psoriatic Lesion Severity Score	Χ¢											Χ¢				Χ¢		Χď			Χq	Χď
Phys. Global Assessment Scale	X											х				X		X			х	x
Skin Biopsy	Х															Х						
Photograph of index lesion	X											Х				х		X			Х	x
Photograph of biopsy lesion e	X															х						

Protocol Activity	Base- line				ı	n Clinic	Period								Oı	ıt Pati	ent V	sits					
					Day 1			Day 2	Day 3	Day 4	Day 8												
				2 hour	4 hour	6 hour	12 hour	24 hour	48 hour	72 hour	168												
	Day -	Pre-	0	post-	Day	Day	Day	Day	Day	Day	Day	Day	Day	Day	Day	Day							
	1	dose	hour	infusion	11	15	18	22	25	29	36 n	43	57	71 n	85	121							
				start																			
Window											±1d	±1d	±1d	±1d	±1d	±1d	±1d	±1d	±2d	±2d	±2d	±2d	±3d
Laboratory Asse	ssmen	ts										_							_				_
Haematology	X٥					X	Χo			Χo	Χo	Χ	X	Х	Х	Х	Χ		X	Χ		Χ	X
Chemistry	Χ					Χf	Χf			Х	Х		Х		Х		Х		Χ	Χ		Х	Х
Urinalysis	Х					Х	Х			Х	Х		Х		Х		Х		Χ	Х		Х	Х
Urine																							\Box
Pregnancy Test (FRP)	Х																X			X		Χ	X
CMV and EBV serology sample	х																						
Viral load sample (CMV, EBV, HSV, VZV) ⁹	х																						
Immunogenicity Sample		Χ									Χ						Χ					χ	
PK Sample h				◀																			
Immune Cell Phenotyping i (Flow)		х				Х		х		Х	Х		х				х		х	X		х	X
Immune Cell Phenotyping ^m (Chip)		х		4-								m											
CD16 and LAG-3 Receptor occupancy		Х				X		X		Х	Х		X				Х		Х	X		Х	x

Protocol Activity	Base- line				ı	n Clinic	Period								0	ut Pati	ient Vi	sits !					
					Day 1			Day 2	Day 3	Day 4	Day 8												
				2 hour	4 hour	6 hour	12 hour	24 hour	48 hour	72 hour	168												
	Day -			post-			Day							Day									
	1	dose	hour	infusion	11	15	18	22	25	29	36 n	43	57	71 n	85	121							
				start																			
Window											±1d	±1d	±1d	±1d	±1d	±1d	±1d	±1d	±2d	±2d	±2d	±2d	±3d
Cytokine Sample		Χ				Х	X	Х	X														
G-CSF Sample		Х				Х		X		X	X		Х				Х		Х	Х		Χ	Х
sLAG-3 Sample		Χ				X		X		Х	X		Χ				Χ		Χ	Χ		Χ	Х
Blood																							
Transcriptomics		Χ						X															
Sample																							
PGx Sample	Х																						

- Continuous 2-lead ECG during infusion. Only significant abnormalities during this time will be databased.
- A targeted physical examination may take place if guided by AE reporting relating to Section 6.3.4, Section 6.3.5 and Section 6.3.6.
- PLSS will be recorded for the index lesion and the biopsy lesion (prior to the biopsy being performed).
- c. d. Index lesion only.
- Photographs of the biopsy lesion will be taken before the skin biopsy.
- Liver Chemistry and CRP only
- Viral load sample for storage as baseline. If symptoms suggestive of viral infection develop then a sample will be taken and analysed with the baseline sample (See Section 6.3).
- See Pharmacokinetic time and events table for dose specific timepoints.
- Additional blood samples may be taken during the study if e.g. subject develops infection (measure LAG-3+ cells), hypersensitivity reactions (serum tryptase), signs/symptoms suggestive of viral reaction, or other parameters as may be clinically or immunologically indicated (See Section 6.3).
- To calculate the correct dose, weight must be measured on Day -1 or Day 1 pre-dose. Triplicate. Only required if screening ECG not within 35 days of Day 1.
- Investigator/designee should remind subjects to comply with contraception requirements on an ~ monthly basis until Follow-Up (either at study visits or by telephone call).
- Immune Phenotyping (Chip) Cohort 7: at Baseline, 6 hours post-start of infusion, Day 8 and 15. Cohorts 8 and 9: at Baseline, 6 hours post start of infusion, Day 43 and 85.
- Additional visit introduced at Day 36 (Cohort 8 only) and Day 71 (Cohort 9 only).

 Samples taken for haematology at Day -1, 12 hours, 72 hours and 168 hours are to include analysis for CD3, CD4 and CD8 lymphocyte subsets.

14.2. Appendix 2: Study Phases and Treatment Emergent Adverse Events

14.2.1. Study Phases for Concomitant Medication

Study Phase	Definition
Prior	If medication end date is not missing and is before 28 days prior to screening visit
Concomitant	Any medication that is not a prior, and up to the last scheduled visit attended (follow-up or combined FU/surveillance)
Off-treatment	Medication started between the last scheduled visit and the surveillance visit will be included in the listing, and flagged.
	5 for handling of missing and partial dates for concomitant medication. Use the rules in itant medication date is completely missing.

14.2.2. Treatment Emergent Flag for Adverse Events

Flag	Definition
Prior	Any starting date before 1st dose
Treatment Emergent	Any starting date between 1st dose and last scheduled visit (follow-up or combined FU/surveillance)
Off treatment	AE occurring between the last scheduled visit and the surveillance visit will be included in the listing, and flagged.
Refer to Appendix completely missing.	5 for handling of missing and partial dates for AE. Use the rules in this table if date is

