Due to the presence of pre-existing ADA in a variable percentage in sera from both healthy and psoriatic human subjects, the initial investigation of GSK2831781 will be carried out initially in ADA negative subjects in Part A of the study to minimise the potential for diluting/confounding a signal of pharmacological or clinical response. However, for GSK2831781 to have development potential, it will need to be used in a mixed ADA population. Therefore, after initial 28 day safety information is available for the DTH cohort at the highest dose for healthy volunteers, an additional cohort of healthy volunteers (without DTH) with pre-existing ADA will be dosed at the same dose level. Subjects in the psoriasis Cohort 7 will be recruited according to the following stratification: 4 ADA negative on active: 2 ADA negative on placebo and 2 ADA positive on active: 1 ADA positive on placebo. Stratification for pre-existing ADAs in subsequent cohorts is not required. Subject follow-up visits will occur when GSK2831781 plasma concentrations are on average around the EC50 value of the *in vitro* depletion assay in human plasma (See Table 1 and Figure 1). This criteria was selected based on the theoretical possibility that GSK2831781 may still be able to deplete LAG-

3+ T cells and affect the immune system, requiring monitoring of infection risk and applying restrictions for immunosuppressives use and travelling to endemic areas. Thus the period between final dosing and follow up will vary depending on the dose received. The time of the follow-up may be revised based on emerging data collected during the study.

In addition, it is not known whether there will be any long term PD effect, beyond the follow-up time at which levels of GSK2831781 would be negligible, for example by prolonged activity due to slow repletion of LAG-3+ cells. Therefore all subjects in Part A will have a 12 month long term surveillance visit for assessment of safety and tolerability, as well as repeat of immune cell phenotyping and other pharmacodynamic assessments, which are still considered clinically abnormal at the follow-up visit. Subjects on lower doses, where follow-up is less than 6 months, will also have an interim 6 month long term surveillance visit. See Section 6.3.5.2 for repeat PPD challenge for subjects with persistent reduction of the DTH challenge.

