14.9.7. Safety Tables

Safety:	Tables				
No.	Population	IDSL / Example Shell	Title	Programming Notes	Deliverable
Advers	e Events (AEs)				
3.1.	safety	CP_AE1P	Summary of all adverse events for healthy volunteers	 by treatment group - 9 groups (including total active) Only TEAE by SOC then PT Notes: Total Active: Total over the 5 doses (except Placebo for HV Combined). ADA status as defined at screening. Combined treatment groups include subjects with ADA-ve and ADA+ve. Only treatment-emergent AEs are summarised: starting date between 1st dose and last scheduled visit (follow-up or combined FU/surveillance) 	IA1 IA2 W2
3.2.	safety	CP_AE1P	Summary of all adverse events for psoriasis patients	Same as for HV - 5 groups (including total active)	IA2 W2
3.3.	safety	CP_AE1P	Summary of drug-related adverse events for healthy volunteers	same output as for all AEs	IA1 IA2 W2
3.4.	safety	CP_AE1P	Summary of drug-related adverse events for psoriasis patients	Same as for HV - 5 groups (including total active)	IA2 W2

Safety:	Safety: Tables					
No.	Population	IDSL / Example Shell	Title	Programming Notes	Deliverable	
3.5.	safety	CP_AE1P	Summary of all adverse events for ADA+ve subjects	1. ADA+ve defined as subject who were ADA+ve at screening visit 2. Parts A and B (cohorts 5, 7-9) => groups: Pbo HV, 0.15mg/kg, Pbo PsO, 0.5mg/kg, 1.5mg/kg, 5mg/kg 3. Only TEAE 4. by SOC then PT	SAC	
3.6.	safety	AE3	Summary of common adverse events for healthy volunteers	1. Common defined as at least 2 patients with the event in any of the treatment groups, separately for parts A and B 2. by treatment group - 9 groups (including total active) 3. Only TEAE 4. by PT	IA2 W2	
3.7.	safety	AE3	Summary of common adverse events for psoriasis patients	Same as for HV - 5 groups (including total active)	IA2 W2	
3.8.	safety	CP_AE1P	Summary of all adverse events (healthy volunteers and psoriasis patients)	Same as for HV or PsO Include 4 columns - Placebo for HV - Total Active (HV) - Placebo for PsO - Total active (PsO)	IA2 W2	

Safety:	Safety: Tables						
No.	Population	IDSL / Example Shell	Title	Programming Notes	Deliverable		
3.9.	safety	AE2	Relationship between system organ class and verbatim text	HV and PsO in the same summary table	SAC		
Serious	Serious Adverse Events						
3.10.	safety	AE1	Summary of serious adverse events for healthy volunteers	 by treatment group - 9 groups (including total active) Only TEAE by PT 	IA1 IA2 W2		

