3.11.	safety	AE1	Summary of serious adverse events for psoriasis patients	Same as for HV - 5 groups (including total active)	IA2 W2		

Safety:	Tables				
No.	Population	IDSL / Example Shell	Title	Programming Notes	Deliverable
Labora	tory: Chemistry	y			
3.12.	safety	LB1	Summary of chemistry by visit for healthy volunteers	 by treatment group - 8 groups By visit, from baseline to last scheduled visit (excluding surveillance visit) 	IA1 IA2 W2
3.13.	safety	LB1	Summary of chemistry by visit for psoriasis patients	Same as for HV - 4 groups	IA2 W2
3.14.	safety	LB3	Summary of change from baseline in chemistry by visit for healthy volunteers	 by treatment group - 8 groups All post-baseline visits, excluding surveillance visits 	IA1 SAC
3.15.	safety	LB3	Summary of change from baseline in chemistry by visit for psoriasis patients	Same as for HV - 4 groups	SAC
Labora	tory: Hematolo	gy			
3.16.	safety	LB1	Summary of haematology by visit for healthy volunteers	same output as for chemistry parameters	IA1 IA2 W2
3.17.	safety	LB1	Summary of haematology by visit for psoriasis patients	same output as for chemistry parameters	IA2 W2
3.18.	safety	LB3	Summary of change from baseline in haematology by visit for healthy volunteers	same output as for chemistry parameters	IA1 SAC
3.19.	safety	LB3	Summary of change from baseline in haematology by visit for psoriasis patients	same output as for chemistry parameters	SAC

Safety:	Tables				
No.	Population	IDSL / Example Shell	Title	Programming Notes	Deliverable
Laborat	tory: Urinalysis	.			
3.20.	safety	UR3	Summary of urinalysis dipstick results by visit for healthy volunteers	 by treatment group - 8 groups By visit, from screening to last scheduled visit (excluding surveillance visit) 	IA1 SAC
3.21.	safety	UR3	Summary of urinalysis dipstick results by visit for psoriasis patients	Same as for HV - 4 groups	SAC
ECG					
3.22.	safety	EG1	Summary of ECG findings by visit for healthy volunteers	1. by treatment group - 8 groups 2. By visit, from screening to last scheduled visit (excluding surveillance visit) 3. For screening, use the worst finding out of the 3 values – add the following footonote for screening visit only: At screening, the finding for a subject is the worst finding observed across the 3 findings.	IA1 IA W2
3.23.	safety	EG1	Summary of ECG findings by visit for psoriasis patients	Same as for HV - 4 groups	IA W2

Safety:	Tables				
No.	Population	IDSL / Example Shell	Title	Programming Notes	Deliverable

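### Events that start after a separate follow-up visit reach no AE or SAE incidence table, only flagged appendix listings; this touches 49 to 58 of the 67 planned subjects

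*SAP*

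**What the plan says.** **The window.** SAP 14.2.2 defines a treatment-emergent event as "Any starting date between 1st dose and last scheduled visit (follow-up or combined FU/surveillance". An event that starts later is labelled off treatment, and its only stated destination is this: "AE occurring between the last scheduled visit and the surveillance visit will be included in the listing, and flagged".

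**The tables.** The notes to Table 3.1 in SAP 14.9.7 state: "Only treatment-emergent AEs are summarised: starting date between 1st dose and last scheduled visit". The healthy-volunteer SAE table (3.10) is specified as "by treatment group - 9 groups (including total active) Only TEAE by PT", and the psoriasis SAE table (3.11) follows it. Drug-related events (Table 3.3) are to be the "same output as for all AEs". No table of events after follow-up is listed.

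**The listings.** Listings 5 to 8 (SAP 14.9.13) give all AEs and all SAEs for both populations. SAP 14.4.2 keeps subject-level listings out of the body of the study report and places them in the appendices.

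**Why surveillance exists.** Protocol 3.3.1 says it is unknown whether there is a pharmacodynamic effect after drug levels have become negligible, "for example by prolonged activity due to slow repletion of LAG-3+ cells". It therefore gives every Part A subject a 12-month visit for safety and tolerability, with a further visit at 6 months where follow-up falls earlier than that. Protocol 7.1.1 has only the targeted events of Section 3.4 reported and databased between follow-up and surveillance. The risks in that section include infection and autoimmunity.

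**The concern.** Safety is the primary objective and adverse events are a primary endpoint. The surveillance contacts were added to look for late harm, and targeted events from that period go into the database. The SAP then plans no summary of them by dose and placebo.

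A single event matters at these cohort sizes. If one of six active subjects in a cohort had a serious infection two months after follow-up, that dose column of the SAE table would still read 0/6. A reader of the main report would have to go to an appendix listing to learn otherwise. The opposite result suffers too: if no late events occur, no table records that by dose, or says how many subjects were observed and for how long.

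**Working it through.** This concerns definitions and display scope, so the plan has no sample-size or power figure to reproduce. The check has three steps.

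**1. Which AE tables admit an event after follow-up?** Read from the programming notes in SAP 14.9.7.

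- Tables 3.1, 3.5, 3.6 and 3.10 state the treatment-emergent restriction.
- Tables 3.2, 3.3, 3.4, 3.7, 3.8, 3.11, 3.36 and 3.37 inherit it by reference to another table.
- Table 3.9 states no restriction, but it maps verbatim text to system organ class and is not an incidence table.

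No incidence table admits such an event. SAP 3.2 does count a surveillance telephone call among the final scheduled visits. However, the definition in 14.2.2 names only the follow-up or combined visit, and its off-treatment row would be empty if the window ran on to the surveillance contact.

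**2. Which subjects have a surveillance period outside the window?** Planned numbers are from Protocol Table 1 and Section 4.1. The visit structure is from the footnote to Table 1 and Section 3.3.1.

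- Part A: all 40 (26 active).
- Cohort 7: all 9 (6 active). Follow-up was at Day 230, with a later 12-month visit or a surveillance call.
- Cohort 8: those already followed up when Amendment 10 was approved. The number is not given, so 0 to 9 (0 to 6 active).
- Cohort 9, and the rest of Cohort 8: none. The single combined visit at Day 183 is itself the end of the window.

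Total: 40 + 9 + (0 to 9) = 49 to 58 of 67, which is 73% to 87%. Active: 26 + 6 + (0 to 6) = 32 to 38 of 44. Unaffected: 9 to 18 subjects.

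**3. How much Part A observation lies outside the window?** Follow-up days are from Protocol Table 1. Observation to 365 days is assumed for everyone. Share outside = (365 − follow-up day) / 365.

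| Cohort | Subjects (active) | Follow-up, days post-dose | Days outside | Share outside |
|---|---|---|---|---|
| 1 | 2 (1) | 28 | 337 | 92% |
| 2 | 2 (1) | 42 | 323 | 88% |
| 3 | 8 (6) | 84 | 281 | 77% |
| 4 | 8 (6) | 146 | 219 | 60% |
| 5 | 12 (6) | 190 | 175 | 48% |
| 6 | 8 (6) | 190 | 175 | 48% |

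Tabulated person-days = 2×28 + 2×42 + 8×84 + 8×146 + 20×190 = 56 + 84 + 672 + 1,168 + 3,800 = 5,780.

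Total = 40×365 = 14,600. Tabulated share = 5,780 / 14,600 = 40%. Outside = 8,820 / 14,600 = 60%.

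On the same basis Cohort 7 has 365 − 230 = 135 days outside (37%), fewer where Amendment 10 replaced the 12-month visit with an earlier call.

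**The case against.** The strongest reply is that this is a matter of display and that no data are lost. Late AEs and SAEs are in Listings 5 to 8 with a flag. With one to six active subjects per cohort, no hypotheses and descriptive safety summaries, a listing identifies a single late SAE. Nor do conduct decisions rest on the SAE table: under Protocol 5.5 one attributable SAE halts escalation, and one infection SAE triggers a temporary halt and review whatever its assessed cause. All of that stands, and it limits the weight of the point. It does not explain why data collected for the primary objective have no by-dose summary.

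A second reply is that there are good reasons to keep the period apart. After follow-up only targeted events are collected. Observation runs roughly against dose: about 365 days in Part A but about 183 at 5 mg/kg. Protocol 3.3.1 no longer mandates lifestyle and medication restrictions and warns of confounding by immunosuppressants or experimental medicines. This also stands, and it rules out one tempting remedy, which is to count every SAE from dose to last contact as a single rate by dose. It argues for a separate display, not for none.

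The magnitude needs care as well. The 92% is one active and one placebo subject at the lowest dose, and 14 of the 40 Part A subjects are on placebo. The 0/6 example does not apply to Cohorts 1 and 2, which have one active subject each.

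**Conclusion.** The point holds for subjects with a separate surveillance contact: 49 to 58 of 67 planned. For them, an AE or SAE with onset after follow-up enters no incidence table. In Part A this leaves 60% of planned person-days outside the tables. That figure assumes full planned enrolment, no early loss, nominal follow-up days and 365 days of observation. Those person-days carry targeted collection only, so the 60% measures time and not expected events.

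A reader might infer more than the documents support:

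- **That late harm goes untabulated at every dose.** It does not. For Cohort 9, and Cohort 8 subjects with the combined visit, events up to about Day 183 are treatment-emergent. At 5 mg/kg drug is expected to be below quantitation by Day 85, so about 183 − 85 = 98 later days are tabulated.
- **That anything discovered at surveillance is excluded.** Onset date governs. An event found then but starting before follow-up is tabulated.
- **That late events vanish from the report.** They are listed and flagged.
- **That laboratory summaries drop planned surveillance results.** This is not shown. Protocol Table 6 schedules haematology and chemistry at the combined visit and none at the telephone call. Section 3.3.1 does not specify routine haematology or chemistry for the separate Part A surveillance visits.

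The result is an inexpensive reporting improvement worth making. It is not a flaw in safety monitoring or data capture.

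**What to change.** Keep the treatment-emergent tables as they are. Add one by-treatment table of SAEs and targeted AEs with onset after the follow-up visit. A clearly separate row or column beside Tables 3.10 and 3.11 would also serve, provided it is not pooled into the treatment-emergent rate. The denominator should be the number of subjects in each group who had a separate surveillance contact, and the table should show the length of that period.

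The cost is SAP wording and one extra output, since the events are already databased and flagged. The downside is that the table needs a careful footnote: only targeted events were collected after follow-up, observation length differs by cohort, and medication restrictions no longer applied. No clinical rule changes.

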14.3. Appendix 3: A&R Data sets

14.3.1. Subject-Level Variables

14.3.1.1. ADA Status

ADASTACD/ADASTAT should be included in POP, AE plus any other data sets with outputs split by ADA status.

- If a subject has one "positive" record for the confirmatory assayin IMGEN (IGSCATCD=2 and IGORRSCD=1) at screening then set to positive (ADASTATCD=1 / ADASTAT="ADA Positive")
- Otherwise set to negative (ADASTATCD=2 / ADASTAT="ADA Negative")

14.3.1.2. Treatment

TRTCD/TRTGRP should be completed as specified in RAP Section 5.1.

Complete as follows:

- 1. Merge DM data sets RAND and RANDALL by RANDNUM to get the PTRTGRP and SCHEDNUM/SCHEDTX for each SUBJID.
- 2. TRTCD/TRTGRP are then completed from PTRTGRP and SCHEDNUM as described below.
- 3. Check the ADA status (IMGEN screening data) of all subjects compared with the treatment group assignment.
- 4. Unrandomised subjects (i.e. subjects with no RANDNUM) will have TRTCD/TRTGRP missing.
- 5. The actual treatment variables ATRTCD/ATRTGRP should just be copied from TRTCD/TRTGRP unless any subject is known to have taken the wrong treatment. In addition, ATRTCD/ATRTGRP can be set to 888/"No Treatment" for untreated subjects as in the SPOTFIRE version of POP.

14.4. Appendix 4: Data Display Standards & Handling Conventions

14.4.1. Reporting Process

Software										
The currently supply	ported versions of SAS software will be used.									
Reporting Area										
HARP Server										
HARP Compound										
Analysis Datasets										
Analysis datasets	Analysis datasets will be created according to Legacy GSK A&R dataset standards.									
Generation of RTF Fi	Generation of RTF Files									
RTF files will be get a second control of the second control	enerated for Interim 2 and SAC.									

